#### 3. STUDY OVERVIEW

This research study is designed to evaluate a new strain of *Streptococcus salivarius* containing probiotic properties for its effect on gingivitis including the oral neutrophil phenotype and oral microbiome modulation during an induced gingivitis state. A 7-week (8 appointments, 7 weeks) clinical study will be conducted to evaluate a probiotic for therapeutic effects that aim to delay the onset of experimental gingivitis and hasten the resolution of the disease.

#### 4.2 Study Population

Advertisements (Appendix 2) will be placed at University of Toronto downtown campus to invite volunteers who are interested to participate. All study participants will undergo informed consent process, prior to enrollment in the study. Categorization of participants and sites will be based on the clinical assessments. Other than the study-related oral health history recorded, there is no intention to obtain information from the participants" other dental or medical records. Sixty (60) qualifying volunteers that agree to participate and sign all corresponding forms will be enrolled.

The first participant will be assigned a number, and all the following enrolled participants will be assigned consecutive numbers by accession. The following inclusion and exclusion criteria will be utilized in this study.

#### 4.3 Inclusion Criteria:

- 1) Male or female volunteers aged 18-70 years
- 2) In good general health, ASA I
- 3) No clinical signs of gingival inflammation at >90% of sites observed
- 4) Absence of Periodontal Pockets, Probing Depth (PD) < 3.0 mm on all teeth/site
- 5) Absence of Clinical Attachment Loss (CAL) = 0 mm
- 6) No periodontal disease history
- 7) Have at least 20 gradeable teeth
- 8) Non-smokers
- 9) Fluent in English
- 10) For study participants of childbearing potential, both men and women, at least one of the following birth control measures must be used: abstinence, hormonal birth control (oral, injectable, transdermal, intra-vaginal), intrauterine devices, confirmed successful vasectomy, or condoms.

#### 4.4 Exclusion Criteria:

1) Presence of orthodontic bands.

- 2) Presence of partial or full dentures.
- 3) Tumour(s) of the soft or the hard tissues of the oral cavity.
- 4) Cavitated carious lesions requiring immediate restorative treatment.
- 5) History of allergy to a consumer or personal care products or dentifrice ingredients as determined by the dental profession monitoring the study.
- 6) Participation in any other clinical study or test panel within one month before entering the study.
- 7) Medical condition which requires pre-medication before dental visits/procedures
- 8) Current use of anti-inflammatory, antibiotics, or antimicrobial drugs or within the last 30 days of enrolment.
- 9) History of periodontal disease.
- 10) History of systemic inflammatory, immune conditions and immunocompromised conditions
- 11) Pregnant or nursing women or those planning to get pregnant
- 12) Use of tobacco products.
- 13) Long-term antibiotic or anti-inflammatory therapy.
- 14) Medication or Natural Health Products (NHPs) that could affect the gingiva like calcium channel blockers, anti-epileptic therapy etc.
- 15) Medical condition or any current usage of medication that the investigator considers may compromise the study participant's safety as well as the quality of the study results
- 16) Allergy to any of the following ingredients: Streptococcus Salivarius, Sorbitol, Isomalt, Calcium phosphate dibasic, Potato starch, Mint, Glyceryl dibehenate, Stevia, Maltodextrin
- 17) Use of other probiotics
- 18) Taking anticoagulant medications and those suffering from blood and bleeding disorders
- 19) Recently experienced or will be experiencing dental, oral or any type of surgery.
- 20) Use of anti-plaque/ anti-gingivitis products
- 21) Presence of active infections
- 22) Participants who are experiencing nausea, fever, vomiting, bloody diarrhoe or severe abdominal pain.
- 23) Use of any antibiotics.

#### 4.5 Continuing Criteria

Each study participant must meet continuance criteria at each visit in order to continue in the study. Study participants will be released from further participation for the following reasons:

- use of non-study dentifrice during treatment periods (acceptable dentifrice will be provided during the study)
- use of oral care products (other than those permitted) during the treatment periods including mouth rinse products and chewing gum.
- non-compliance with study procedures
- actively participating in another clinical study unless permission has been granted by the Principal Investigator
- development of a medical condition or taking a medication which would affect the study outcome (such as an antibiotic) as detailed in the exclusion criteria.
- Subject fails to substantially comply with the protocol requirements.
- Subject fails to report for a scheduled examination.

- Subject is treated with medications during the course of the study, which may interfere with the parameters of the study.
- Subject develops an adverse reaction. The study Investigator will immediately notify the study monitor and information will be recorded on Adverse Reaction Form.
- Subject receives emergency dental or medical treatment, which may interfere with the parameters of the study.
- · Sponsor elects to terminate the study.
- Subject elects to terminate participation in the study. No pregnant women will intentionally
  be enrolled in this study. All female subjects being considered for this study will be asked
  about their pregnancy status. the clinical/research investigator if they become pregnant
  during the course of the 9-week study. In the event a woman enrolled in this clinical
  research study becomes pregnant at any time during this study, participation in this study
  will be terminated upon the clinical staff's notification of the event.

•

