#### 9.0 REPORT OF ADVERSE EVENTS

Study participants will be told of any possible adverse reactions or side effects from exposure to this method or product. Oral irritation is possible. If side effects occur, it is expected to be mild and temporary. Any event will stop when the study participant stops being exposed to the instrument or returns to their normal oral hygiene. At all examinations, each participant will be asked if they have experienced any discomfort or oral irritation. The investigators will record any and all adverse reactions and report this documentation to the Product Safety Assurance Department. The nature of the reaction and any correlation with product usage will be assessed. If the evidence indicates that the adverse reaction may be due to product usage, the study participant will be instructed to discontinue product use and appropriate treatment will be provided. In the event of an adverse experience, emergency or other problems or questions regarding your participation in this study participants can contact the following investigators:

[name] at [contact] [name] or the Research Oversight and Compliance Office - Human Research Ethics Program at [contact] or [contact] In the event of a medical emergency, please contact your physician

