# 9.2 Documenting and Reporting Adverse Events

#### 9.2.1 General Procedures for All Adverse Events

All clinical complaints, symptoms, or signs that meet the adverse event definition will be recorded on the Adverse Reaction Form (Appendix VIII) using a recognized medical term or diagnosis that accurately reflects the event. Source documentation should be maintained that allows for clear identification of each adverse event and the following parameters required for the form:

- AE description
- Date of onset
- Date of resolution
- Outcome
- Severity
- Seriousness
- Relationship to study drug (causality)
- Actions taken

Adverse events will be assessed by the investigator or designee for severity, relationship to the study product, possible etiologies, and whether the event meets the criteria as a serious adverse event and therefore requires immediate notification of the sponsor.

For data collection purposes, the outcome of all adverse events recorded on the Adverse Reaction Form will be designated as of the completion of the final evaluation or examination. However, the investigator is responsible for following all adverse events until resolution or until no longer of clinical concern, and providing these data to the sponsor.

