# 12.2 Study participant Termination/Procedures

A genuine effort will be made to determine the reason(s) why a study participant fails to return for the necessary visit(s) or is dropped from the study. Study participants could be dropped from the study if any of the following occur:

- 1. Study participant fails to substantially comply with the protocol requirements.
- 2. Study participant fails to report for a scheduled examination.
- 3. Study participant is treated with medications during the course of the study, which may interfere with the parameters of the study.
- 4. Study participant develops an adverse reaction. The study Investigator will immediately notify the study monitor and information will be recorded on Adverse Reaction Form.
- 5. Study participant receives emergency dental or medical treatment, which may interfere with the parameters of the study.
- 6. Sponsor elects to terminate the study.
- 7. Study participant elects to terminate participation in the study.

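### Section 4.5 makes release mandatory where section 12.2 makes it optional, most sharply for one missed examination or any adverse reaction, and the visible text provides for no outcome data after release.

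*Protocol*

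**What the plan says.** Section 4.5 sets a condition for staying in the trial: "Each study participant must meet continuance criteria at each visit in order to continue in the study". It continues: "Study participants will be released from further participation for the following reasons". The list includes "Subject fails to report for a scheduled examination", "Subject develops an adverse reaction" and "non-compliance with study procedures", none with a threshold or a severity qualifier.

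Section 12.2 covers much of the same ground in permissive terms: "Study participants could be dropped from the study if any of the following occur". Section 12.3 is mandatory again for any antibiotic, and for emergency dental treatment that the monitor thinks could affect the study measurements.

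Section 9.0 expects side effects to be mild and temporary. Where a reaction may be due to the product, "the study participant will be instructed to discontinue product use and appropriate treatment will be provided". It does not say that the participant leaves the trial. On safety follow-up, section 9.2.1 says that "the investigator is responsible for following all adverse events until resolution or until no longer of clinical concern".

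**The concern.** Two sections prescribe different consequences for the same event. A site that follows 4.5 removes a participant who misses one examination or reports mild irritation. A site that follows 12.2 may keep that participant. Two people with the same event can therefore be treated differently, with no stated basis for the choice.

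What is at stake is outcome data. Section 8.0 compares clinical indices and neutrophil counts on Days 0, 7, 14, 21, 28 and 35. If release ends the examinations, the later values do not exist, and no choice of analysis set or missing-data method brings them back. These events happen after randomisation. An adverse reaction, or medication taken for one, could be related to the lozenge or to the degree of inflammation, so the participants who remain may no longer be comparable between groups.

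**Working it through.** The check is mainly textual. The protocol states no rate or loss figure to reproduce.

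**Step 1. Compare the trigger lists.** All seven reasons in 12.2 also appear in 4.5, where release is mandatory; in 12.2 it is optional.

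| Reason | Qualifier in both sections | Other text |
|---|---|---|
| Missed examination | None | 12.2 asks only for the reason for non-return |
| Adverse reaction | None | 9.0 and both event forms foresee other courses |
| Substantial non-compliance | Judgement of what is substantial | Missed Doses section tolerates a skipped lozenge |
| Interfering medication | Only if it may interfere | Concomitant Therapy section gives the investigator discretion; 12.3 is mandatory for antibiotics |
| Emergency treatment | Only if it may interfere | 12.3 is mandatory for dental treatment, subject to the monitor's opinion |
| Sponsor ends the study | Not applicable | No practical conflict |
| Participant's choice | Not applicable | No practical conflict |

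Of the seven, 7 − 2 = 5 are participant events with a real difference in wording. Three of the five already contain judgement wording that narrows the gap, so 5 − 3 = 2 remain both shared and unqualified: the missed examination and the adverse reaction. The unqualified non-compliance item is in 4.5 only, so it is not part of the conflict with 12.2.

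**Step 2. Adverse reactions elsewhere.** Section 9.0 stops product only when the reaction may be due to it, so its use of the term also covers reactions that are not. The non-serious event form (Appendix 8) records what was done with the product (continued, reduced, stopped temporarily or stopped) separately from whether the protocol was continued, and asks whether the event returned on reintroduction. The serious event form lists continuing the protocol, stopping the product and excluding the participant as different actions. All of this presupposes that someone can have an event, or even stop product, and remain in the study. Mandatory release under 4.5 leaves no room for that.

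**Step 3. What is provided after release.** Gingival index, bleeding, plaque index, probing depth, crevicular fluid, plaque, saliva and rinse samples are scheduled only at Visits 1 to 8 (sections 6.5.1 to 6.7.3). After release the visible text provides for finding the reason for non-return (12.2), following adverse events (9.2.1, 9.2.2), pregnancy contact (12.4) and the Study Participant Withdrawal Form, which has no fields for indices or samples. No efficacy measurement is provided for.

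**Step 4. Loss per released participant.** Release at Visit v removes 8 − v later visits.

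- Release for missing Visit 2 (Day −7): 8 − 2 = 6 visits, which are all six time points in section 8.0.
- Release at Visit 4 (Day 7): 8 − 4 = 4 visits (Days 14, 21, 28 and 35), four of the six.
- Release at Visit 6 (Day 21): 8 − 6 = 2 visits (Days 28 and 35), two of the six.

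The number of participants affected cannot be derived, since no rate is given for missed visits, reactions or any other trigger.

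**The case against.** The strongest reply is that the adverse-event forms show that participants are meant to stay after an event, so outcomes may well be collected in practice, and that no sentence forbids it. This partly stands: the loss is inferred from release from participation together with the absence of any provision. But the forms then contradict 4.5 rather than cure it, and they say nothing about missed visits.

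Several stronger readings are tempting and are not supported:

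- *All the shared triggers conflict equally.* They do not. Medication, emergency treatment and substantial non-compliance already allow judgement.
- *The Study Termination Form proves that no indices are taken at exit.* It holds only a medication history and a normal/abnormal tissue check, but indices are always recorded on the separate Oral Assessment Form, so their absence proves little.
- *The protocol rules out later collection altogether.* Only the visible text can be judged. Figure 1 and the text just before section 4.2 were not in the copy read.
- *Data already collected are discarded.* Nothing says so.
- *A given percentage of the 60 participants will be lost.* Any such figure rests wholly on an assumed miss rate.
- *The payment rule in section 10 must change as well.* Resolving this conflict does not require it.

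It can also be argued that, in an induced-gingivitis model, antibiotics or interfering treatment distort the outcome, so removal is a defensible design preference. That stands as a reason not to prescribe the result for those triggers. It does not apply to a single missed visit.

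**Conclusion.** The concern holds in limited form. Sections 4.5 and 12.2 cannot both be followed, and the conflict is clearest for a single missed examination and for any adverse reaction. Mandatory release also contradicts section 9.0 and the two event forms. Followed literally, 4.5 loses between two and six of the six comparison time points for a participant released between Visit 2 and Visit 6. The total loss and its direction are unknown. That the loss may be selective is a reasonable possibility, not something the protocol demonstrates. The conclusion assumes that release means no further study examinations and that no unseen text provides otherwise. It cannot be left to a SAP, because it concerns whether data are collected at all. The sponsor should correct it. It does not by itself invalidate the design.

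**What to change.** Reconcile sections 4.5, 9.0, 12.2 and 12.3, both adverse-event forms and the Study Participant Withdrawal Form, and state separately what ends product use and what ends follow-up.

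- **Missed visit or adverse reaction:** state that neither by itself ends data collection. The event is recorded, and the remaining scheduled examinations and samples are taken unless consent is withdrawn or the investigator judges this unsafe.
- **Antibiotics, interfering medication, emergency treatment:** reconcile the passages and state whether scheduled outcome data are still collected and flagged.
- **Left to the sponsor:** when the lozenge or the no-hygiene period stops is a clinical matter outside this change.

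The cost is amendment wording, its approval under section 12.7 and edits to the forms. No visits are added to the eight already planned. The downside is that off-product or non-compliant observations enter the data set, so they must be flagged and their handling set out in the SAP.

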# 4.6 Concomitant Therapy

If a study participant takes concomitant medications as a matter of necessity for the treatment of a medical condition, then such medication may be permitted for the duration of the study at the discretion of the investigator. However, it is the responsibility of the investigator to disqualify from entering the study any study participant who, upon screening, is using medication or consumer product that might obscure the interpretation of study results. All medications currently used by the study participant at enrollment, or any time through the end of the study, will be recorded on the visit report form (Appendix VI). Study participants may receive medication to treat adverse events as deemed necessary by the investigator or the study participant's physician.

#### 4.6 Missed Doses

If a study participant misses their dose, they will be asked to take it if no more than 3 hours has passed since they brushed their teeth. If more than 3 hours have passed, they will be asked to skip the dose completely. Do not double up on the next dose. Do not exceed 2 lozenges per day.

#### 5. TEST PRODUCTS/INTERVENTIONS

Each participant randomized to the intervention group will receive mint-flavoured SALI-10 lozenges. They will be instructed to take a lozenge twice daily after brushing by letting it dissolve in the mouth. The participants will be using the SALI-10 lozenges throughout the study.

# 5.1 SALI-10 Lozenges Manufacturer Information

The placebo and probiotics lozenges will be manufactured by Lallemand Health Solutions, [name]

[contact]

Content of the placebo lozenge:

Excipients	Content per 1 gram- lozenge (in mg)
Sorbitol	310
Isomalt	310
Maltodextrin	175
Potato starch	90
Dibasic calcium phosphate	83
Mint flavour	20
Glyceryl dibehenate	10
Steviol glycosides	2

# Content of the probiotic lozenge:

Active ingredient	Content per 1 gram- lozenge (in mg)
Streptococcus salivarius	200* Min. Bi CFU/lozenge at manufacturing
Excipients	
Sorbitol	310
Isomalt	310
Dibasic calcium phosphate	83
Potato starch	QSP (65*)
Mint flavour	20
Glyceryl dibehenate	10
Steviol glycosides	2

# 5.2 Dispensing, Storage, and Accountability

All product(s) are distributed by the study coordinator at the clinical test site. The study participant will follow provided instructions on when and how to brush their teeth. These instructions are explained in the procedure section.

One of the study personnel, [name], will be responsible for dispensing and collecting the containers of the SALI-10 lozenges at each visit.

# 6. STUDY PROCEDURES

# 6.1 Randomized Assignment and Product Blinding

Qualified study participants will be randomly assigned to one of two study groups, either Group A or Group B, using randomization software. To maintain blinding, the manufacturer will produce both probiotics and placebo lozenges, dispense them in identical, opaque bottles, and label them as either Group A or Group B. The assignment of probiotics to one of these groups will be determined by the manufacturer and disclosed only at the study's conclusion. Each bottle will be labeled with a code (either letter A or B, followed by a number) and emergency contact information. The products will be distributed in sealed boxes that look identical to prevent any differences in appearance or packaging between study groups. Each product inside the box will be overwrapped and include instructions for at-home use and safety information, including emergency contact details.

To monitor study participant compliance, the investigators will use a pharmaceutical scale to ensure the number of lozenges remaining in the bottle matches the expected count at each study visit. A scale will be used to avoid the operator from seeing the lozenges, in order to preserve blindness in this study (placebo and probiotic lozenges are not perfectly identical).

Study participants will be assigned a unique identification number in chronological order (e.g., from 1 to 60) as they enroll in the study. These identification numbers have been pre-assigned to a study group based on a computer-generated randomization list provided by an independent statistician. Cohabitant study participants will be assigned to the same study group and receive the same products. Study participants will be instructed to avoid using any other oral hygiene products. There will be no dietary restrictions during the study.

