# 6.7.3 Visit 8 End of Study (t5) (Day 35)

The study participants will return the containers containing the lozenges to a member of the study team. Study participants will then undergo an oral hard and soft tissue exam as well as measurements of probing depth (PD), attachment level (AL), visible plaque index (VPI), gingival index (GI) and bleeding on probing (BOP) and recorded on the Oral Assessment Form (Appendix 7). The biospecimen collection will include gingival crevicular fluid (GCF), plaque, saliva and a saline oral rinse. The study participants will be informed that this is the end of the study. They will be given their compensation and told that they may resume their regular oral hygiene. Once the study has been completed, the manufacturer will reveal to which group was the probiotic assigned to (either A or B). Afterwards, the investigators will inform participants to which group they were assigned and will ask for their feedback in regards to their experience. Researchers will query participants on their use of NHPs, as well as any adverse effects they experienced.

Please refer to figure 1. Illustrating the breakdown and timeline of the study as well as the relevant study procedures at each time point and the objectives.

Figure 1. Study Flow Infographic

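### The arm letter is printed on every bottle under a single A/B key, so one confirmed disclosure of that key exposes all 60 allocations to site staff who know the letters

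*Protocol*

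**What the plan says.** Section 4.2 sets the enrolment: "Sixty (60) qualifying volunteers that agree to participate and sign all corresponding forms will be enrolled". Section 6.1 describes the allocation: "Qualified study participants will be randomly assigned to one of two study groups, either Group A or Group B, using randomization software". The manufacturer makes both products and labels the bottles by group, and on the label itself: "Each bottle will be labeled with a code (either letter A or B, followed by a number) and emergency contact information". Which of the two groups receives the probiotic "will be determined by the manufacturer and disclosed only at the" study's conclusion. Section 6.7.3 confirms that unblinding is one A-or-B statement, after which "the investigators will inform participants to which group they were assigned".

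The labelled bottles pass through site hands throughout. Under Section 5.2 one member of the study personnel "will be responsible for dispensing and collecting the containers of the SALI-10 lozenges at each visit". For compliance, Section 6.1 says "the investigators will use a pharmaceutical scale to ensure the number of lozenges remaining in the bottle" agrees with the expected count at each visit. The scale is used so that the operator does not see the lozenges, because the "placebo and probiotic lozenges are not perfectly identical".

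Other protections in Section 6.1 are opaque look-alike bottles, sealed look-alike boxes, overwrapping, and allocation of cohabitants to the same group. The serious adverse event form in the appendices has a field recording whether the code was broken, but the Protocol text describes no procedure for breaking it.

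**The concern.** With an arm letter on every bottle, the blind rests on one binary fact for the whole trial. Blinding is normally built so that losing it for one participant costs only that participant. Here it cannot be lost for one without being lost for all, as far as people who know the letters are concerned. A justified safety unblinding of one person would therefore carry a price for the entire study.

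There is a second possible route. The lozenges differ in some visible way. Weighing conceals them from the operator at the compliance check, but participants see them every day. A correct inference about what one letter means would apply to every bottle with that letter. The Protocol does not say how large or how telling the difference is.

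What is at stake is the scoring of gingival index (Section 7.4) and visible plaque (Section 7.3), both judged by an examiner. If an examiner came to know the letters and their meaning, all later scores in both groups would be open to detection bias. The Protocol neither says that this will happen nor contains anything that prevents it.

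**Working it through.** **What is exposed**

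Inputs: 60 participants (Section 4.2); two groups (Section 6.1); one key, namely which letter is the probiotic (Sections 6.1 and 6.7.3).

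1. The code is a letter plus a number. The letter alone gives the group, so the number adds no protection.
2. With two letters and two products, knowing the product behind one letter fixes the other.
3. Staff who dispense, collect and weigh bottles see each participant's letter. For them, one confirmed disclosure determines 60/60 = 100% of allocations.
4. With participant-unique codes and no arm letter, one disclosure directly reveals 1/60 = 1.7%.

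This count needs no assumed parameter.

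**How often it might happen (assumption only)**

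Let each participant have an independent in-study disclosure risk p, which the Protocol does not give. The chance of at least one disclosure is 1 − (1 − p)^60. Expected exposure is 60 × that chance under the two-letter code and 60 × p under unique codes.

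| Assumed p | Chance of at least one | Expected exposed, A/B letters | Expected exposed, unique codes |
|---|---|---|---|
| 0.5% | 26% | 15.6 | 0.3 |
| 1% | 45% | 27.2 | 0.6 |
| 2% | 70% | 42.1 | 1.2 |
| 5% | 95% | 57.2 | 3.0 |

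**What a biased examiner could do (assumption only)**

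Assume no true effect, a two-sample t test at two-sided 0.05, and an examiner who knows the arms and shifts every score so that the arms differ by d standard deviations. With n per arm, the noncentrality is d × √(n/2) on 2n − 2 degrees of freedom. The rejection probability in the favoured direction is P(T > critical value).

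- n = 30 (an assumed even split of 60): √15 = 3.873, 58 df, critical value 2.002.
- n = 25 (assumed): √12.5 = 3.536, 48 df, critical value 2.011.

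| Shift d (SD) | Noncentrality, n = 30 | False-positive rate, n = 30 | Noncentrality, n = 25 | False-positive rate, n = 25 |
|---|---|---|---|---|
| 0 | 0 | 0.025 | 0 | 0.025 |
| 0.05 | 0.194 | 0.038 | – | – |
| 0.10 | 0.387 | 0.057 | 0.354 | 0.053 |
| 0.25 | 0.968 | 0.157 | 0.884 | 0.137 |
| 0.50 | 1.936 | 0.478 | 1.768 | 0.410 |

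**Does the weighing itself reveal the arm?**

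On nominal content it does not. The placebo in Section 5.1 sums to 310 + 310 + 175 + 90 + 83 + 20 + 10 + 2 = 1000 mg, and the probiotic to 200 + 310 + 310 + 83 + 65 + 20 + 10 + 2 = 1000 mg. The weakness lies in the label, not the scale.

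**The case against.** The strongest reply is that nothing here is misstated. The key stays with the manufacturer until the end, no one plans to give it to the site, and the two-letter scheme is internally consistent. Harm needs three further steps: the key leaks during the trial, it reaches an examiner who also knows the letters, and that examiner's scoring shifts. All of this stands, and it is why the point concerns a vulnerability and not an error.

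The code-break field is thin evidence that unblinding is expected. The event forms look like generic templates (the non-serious form offers fabric care as a product category), and Section 9.0 deals with a suspected reaction without any unblinding step. That is fair. However, if a code break is ever needed, the scheme offers no way to limit it to one person.

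The appearance route is uncertain. Each participant sees one product, cohabitants share a group, and seeing one product does not show which is active. That also stands.

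The false-positive table is not a forecast. It shifts every score, whereas a disclosure part-way through affects only assessments still to come. Nor does the detection-bias argument extend to the sequencing, proteomic and chemokine measures, and microbiome modulation is the first objective in Section 2.

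Finally, the disclosure at the end of the study under Section 6.7.3 does not show that examiners know the letters during it, and the statements that a provision is absent apply only to the text available, which lacks the part between Sections 3 and 4.2. Still, nothing in that text hides the letter, separates the examiner from the bottles, or confines the damage once the key is known.

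**Conclusion.** The concern holds. Under the labelling fixed in Section 6.1, one confirmed disclosure of the key exposes 60 of 60 allocations to anyone who knows the letters, against 1 of 60 with participant-unique codes. That result follows from the Protocol's wording alone.

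The effect on inference is conditional and cannot be sized from the Protocol: the disclosure risk, the scoring shift and the arm sizes are all assumed. If no examiner learns the arms, there is no inflation from this source. The point should be corrected because the remedy is simple and the examiner-judged outcomes depend on the blind. It does not show that the blind will fail.

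**What to change.** - Label bottles with kit numbers unique to each participant and without an arm letter. Where a participant receives several bottles, their codes should not share any feature that marks the arm.
- Keep the kit-to-arm list with the independent statistician and the manufacturer only. If the statistician is to remain unaware of which arm is active, the manufacturer alone can hold it.
- Describe in Section 6.1 a code break for an individual participant that discloses no other participant's arm.
- State that clinical examiners do not dispense, collect or weigh bottles and do not see their codes or any assignment log.

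The cost is relabelling kits for about 60 participants, revised wording in Section 6.1 and slightly more dispensing bookkeeping. The Protocol does not give the number of bottles per participant or say whether labels have already been printed, so the exact effort is unknown. A randomization list by participant number already exists under Section 6.1, so little else needs to be set up.
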